**Adoption** is identified as the percentage of providers from the PC clinic who deliver alcohol-related care when a Veteran screens positive for unhealthy alcohol use. Specifically, we will use data available in the EHR to examine delivery of brief interventions, consults placed to PC-MHI/clinical pharmacists or specialty addictions treatment and providing pharmacotherapy for AUDs at the provider and clinic level. Rates of alcohol-related care pre-intervention (2019-2022), during the course of the practice facilitation intervention (July 2022-December 2022), after the intervention (e.g., 3- and 6-months post intervention (Jan 1, 2023-March 31, 2023, and Jan 1, 2023-June 30, 2023 respectively) will be used to measure whether adoption rates of alcohol-related care increased over time.

**Maintenance** is defined as the extent to which evidence-based alcohol care becomes routine and part of the PC culture (care sustained over time). Reach and Adoption outcomes using EHR data will be assessed at 12-months post intervention (Jan 1, 2023-Dec. 31, 2023) to examine whether high-quality alcohol care was sustained.

**Effectiveness** is defined as the prevalence of unhealthy alcohol use at 12-months post-intervention (Jan 1, 2023-Dec. 31, 2023) as measured by AUDIT-C scores pulled from the EHR. This variable will also be expressed as a rate with the denominator defined as all Veterans with a visit to PC during the practice facilitation intervention (same as for Reach outcomes). The numerator will be the number of Veterans with an encounter in PC who screened positive for unhealthy alcohol use (AUDIT-C  $\geq$  5) at 12-months post facilitation intervention. While it is unlikely that a pilot study will have a measurable

impact on clinical outcomes, measuring effectiveness will serve as pilot data for a larger trial.

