#### **5.7 Data Analysis**

**Implementation Outcomes:** Reach outcomes will be reported descriptively (e.g., percentage of patients with an AUDIT-C  $\geq 5$  who were offered a BI or pharmacotherapy for AUD) and compared pre- (2019-2022) and post-implementation (at 3- and 6-months) to see whether Reach of alcohol care increased over time. Adoption outcomes via EHR will be descriptive, and include percentages, frequencies, and means (SD) of alcohol-related care by provider and clinic to understand whether Adoption of high-quality alcohol-related care increased over time. Descriptives will be examined and compared at the start of Active Implementation and at 3- and 6-months post Active Implementation. Reach and Adoption rates will again be examined at 12-months post Active Implementation and compared to rates at 3- and 6-months to see if high-quality alcohol-related care was sustained (Maintenance). **Effectiveness outcomes:** Effectiveness will be assessed via a time-series analysis, where the intervention site will serve as its own control, and we will investigate whether Veterans' with an encounter in Pittsburgh VA Primary Care during the implementation intervention reduced their drinking 12-months post intervention using AUDIT-C scores in the EHR. Time-series analysis was chosen because historical trend is accounted for in the analytic model, results can be displayed graphically, and the size of the effect can be estimated at different times post

intervention. The outcome (AUDIT-C scores) will be modeled using a regression model with an indicator for practice facilitation (pre- vs. post-), a continuous term for time (days since practice facilitation dissemination) and the interaction between the two. The indicator variable will assess immediate changes in AUDIT-C scores post implementation intervention, while the interaction term will assess if there is a change in the slope of AUDIT-C scores pre- and intervention at 12-months. While there is controversy over whether pilot studies should assess clinical efficacy or effectiveness, we decided to examine it here as a training opportunity and as preparation for a possible hybrid effectiveness-implementation Merit trial investigating practice facilitation as a way to improve alcohol-related care on a larger scale.

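### The one comparison labelled Maintenance uses only post-facilitation rates, so taken alone it cannot tell a gain that was kept from no gain, or from one lost when facilitation ended

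*Combined protocol and SAP*

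**What the plan says.** Section 5.1, under the evaluation of the intervention, defines Maintenance as "the extent to which evidence-based alcohol care becomes routine and part of the PC culture (care sustained over time". It continues: "Reach and Adoption outcomes using EHR data will be assessed at 12-months post intervention (Jan 1, 2023-Dec. 31, 2023", the purpose being "to examine whether high-quality alcohol care was sustained". It gives no reference rate and no threshold.

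Section 5.7 supplies the comparison: the 12-month rates are "compared to rates at 3- and 6-months to see if high-quality alcohol-related care was sustained (Maintenance". Section 5.1 dates the 3- and 6-month windows as "Jan 1, 2023-March 31, 2023, and Jan 1, 2023-June 30, 2023 respectively".

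Three other comparisons bear on the point:

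- **Reach, section 5.7:** pre-intervention (2019-2022) is set against "post-implementation (at 3- and 6-months) to see whether Reach of alcohol care increased over time".
- **Descriptives, section 5.7 (directly after the Adoption sentence):** "Descriptives will be examined and compared at the start of Active Implementation and at 3- and 6-months post Active Implementation".
- **Adoption, section 5.1:** rates are planned for the pre-intervention period, "during the course of the practice facilitation intervention (July 2022-December 2022", and afterwards.

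For Reach, section 5.1 lists rates at the start of facilitation and at 3 and 6 months afterwards. The Reach denominator is defined by visits during facilitation, but no rate over that period is among the listed time points.

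**The concern.** Care can be sustained only if it first improved. A contrast among three post-facilitation rates shows whether care drifted during 2023. It does not show whether care was better in 2023 than before July 2022, or what happened between July-December 2022 and early 2023, when facilitation stopped.

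The distinction matters for what follows the pilot. Section 5.5 raises scaling the strategy across VA primary care and section 5.7 mentions a possible larger trial. A strategy that never changed care and one whose effect ended with the facilitator's support call for different next steps. The Maintenance result should help to tell them apart.

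**Working it through.** The plan gives no rate, threshold, margin or sample size for Maintenance, so there is no figure to reproduce. The check asks what each planned contrast shows when the truth is known.

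**Inputs.** The windows are those in section 5.1: 3 months = January-March 2023 (90 days), 6 months = January-June 2023 (181 days), 12 months = January-December 2023 (365 days). The rates are assumed for illustration, with equal numbers per quarter of 2023 (Q1 to Q4).

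**Formulas.** 3-month rate = Q1. 6-month rate = (Q1+Q2)/2. 12-month rate = (Q1+Q2+Q3+Q4)/4.

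| Case (rates in %) | Pre | Jul-Dec 2022 | 3 mo | 6 mo | 12 mo | 12-3 and 12-6 | 3-pre and 6-pre | 12-pre | 12-active |
|---|---|---|---|---|---|---|---|---|---|
| Never improved | 40 | 40 | 40 | 40 | 40 | 0 | 0 | 0 | 0 |
| Fell back to baseline when facilitation ended | 40 | 60 | 40 | 40 | 40 | 0 | 0 | 0 | -20 |
| Fell below baseline | 40 | 60 | 30 | 30 | 30 | 0 | -10 | -10 | -30 |
| Improved and kept | 40 | 60 | 60 | 60 | 60 | 0 | +20 | +20 | 0 |

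**Reading the table.**

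1. The Maintenance contrast (12-3 and 12-6) is 0 points in all four cases.
2. The separate comparison of pre with 3 and 6 months gives 0, 0, -10 and +20. It identifies the case with a lasting gain, but not which of the first two cases occurred.
3. Separating those two needs the July-December 2022 rate: 12-active is 0 against -20. That rate is planned for Adoption and not listed for Reach. The rate at the start of facilitation does not replace it, because it does not show the level reached during facilitation.
4. The last two columns are contrasts that the plan does not name.

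**Effect of the nested windows.** The 3-month window is 90/365 = 24.7% of the 12-month window's days, and the 6-month window is 181/365 = 49.6%. Suppose pre is 40%, active 60%, and the 2023 quarters 60, 60, 40 and 40%. The 12-month rate is (60+60+40+40)/4 = 50%, so the planned contrast is 50-60 = -10 points. July-December 2023 alone is 40%, and 40-60 = -20 points, the true loss. Set against pre, the 12-month rate still shows 50-40 = +10 points, although nothing of the gain remains in the second half of the year (40-40 = 0). Adding a pre-intervention reference without changing the window would therefore not be enough.

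**Effect of the pre period as written.** January 2019-December 2022 is 1,461 days, of which July-December 2022 is 184 (12.6%). With 40% before facilitation, 60% during it and equal volume per day, the pre rate becomes (40×1,277 + 60×184)/1,461 = 42.5%. The reference needs to end before July 2022.

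**The case against.** The Maintenance sentence closes a sequence. Section 5.7 first asks whether Reach rose from pre-intervention to 3 and 6 months, then compares descriptives from the start of implementation, and only then turns to 12 months. A reader with all the results would see that a gain was absent. Where a gain at 6 months was followed by a decline, the net difference from pre-intervention follows by addition. For Adoption, the July-December 2022 rate would show a fall when facilitation ended. The outcomes are descriptive, in a pilot at one site. All of this stands. It narrows the point to two gaps: the 12-month rate is never set against the pre or active period, and Reach has no active-period rate.

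Three stronger readings are tempting and not supported:

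- **A reader might infer that care which never improved would be reported as sustained.** The plan has no rule that turns a 0-point contrast into that word. 'Could be' is as far as the text goes.
- **A reader might infer that the contrast also errs the other way, calling a partly kept gain lost.** Take assumed rates of 30% pre, 45% at 3 and 6 months and 38% at 12 months. It looks as if (38-30)/(45-30) = 53% of the gain remains. But the 12-month window contains the 6-month one. With equal volume per day, July-December 2023 is (38×365 - 45×181)/184 = 5,725/184 = 31.1%, which leaves 1.1/15, about 7%. Under the plan's own windows, 'not sustained' would be a fair description.
- **A reader might assume that gains are usually lost when the facilitator withdraws.** Nothing in the documents says so. The step matters because the Maintenance contrast leaves it out, not because loss there is known to be common.

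**Conclusion.** The point holds in a limited form. The only contrast labelled Maintenance gives the same answer, 0 points, for a gain that was kept, for no gain, and for a gain lost when facilitation ended. A flat 2023 could therefore be described as sustained without support. The planned comparison of pre with 3 and 6 months would reveal for Reach that no lasting gain exists, so the error would not be hidden. What remains unanswerable from the planned contrasts is whether Reach never improved or improved and then fell back. For both outcomes, the 12-month rate is also never directly tied to the pre-intervention or active level.

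The four-case result follows from the structure of the contrast and does not depend on the assumed percentages; the sizes of 10, 20 and 30 points do. This is a worthwhile, inexpensive improvement to a descriptive pilot outcome. It does not invalidate the study.

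**What to change.** In sections 5.1 and 5.7:

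1. Calculate Reach, as well as Adoption, over July-December 2022.
2. For Maintenance, take a late-2023 rate from a window that does not overlap the 3- and 6-month windows. July-December 2023 would do, and it covers the same calendar months as the active period.
3. Compare that rate with the pre-July 2022 rate and with the July-December 2022 rate, as differences with confidence intervals. Keep the 3- and 6-month rates as intermediate points.
4. Use the word 'sustained' only if a gain over the pre-July 2022 rate was first shown and the late-2023 rate remains above that rate. State in advance what counts as shown, so that a trivial excess does not qualify.
5. If a share of the gain retained is reported at all, make it secondary, because it is unstable when the gain is small.

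The cost is about a paragraph of text. The January 2019-December 2023 data pull already covers every period. The downside is that no Maintenance claim can be made if there was no initial gain.

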### **Evaluation of the Practice Facilitation Intervention: Implementation and Clinical Outcomes.**

Aim 3 implementation and clinical-specific outcomes were derived guided by the RE-AIM (Reach, Effectiveness, Adoption, Implementation, and Maintenance) evaluative framework, often used to guide implementation evaluations. RE-AIM will be assessed using EHR data pulled from VA's Corporate Data Warehouse (CDW). The data pull will include data from January 1, 2019 – December 31, 2023, to evaluate these outcomes, which includes the pre-intervention period, the active facilitation intervention period, and the post-facilitation intervention period (i.e., 3-, 6-, and 12-months after active implementation). RE-AIM constructs are defined as follows:

**Reach** of alcohol-related care will be assessed at the patient level using EHR data, pulled from VA's CDW. **Reach** outcomes will be expressed as a rate, with the

denominator (for all outcomes) defined as all Veterans with a visit to the Pittsburgh VA primary care clinic during the practice facilitation intervention. The numerator for each Reach outcome is as follows: the number of Veterans who screened positive for unhealthy alcohol use (AUDIT-C  $\geq$  5) AND had any documented brief intervention, encounters with primary care-mental health integration (PC-MHI), encounters with PACT/ Whole Health clinical pharmacists, specialty addictions treatment (inpatient and outpatient clinic visits for substance use disorder treatment encounters with an accompanying AUD diagnosis), or pharmacotherapy for AUD (any filled prescription for FDA-approved medications: acamprosate, disulfiram, or oral/injectable naltrexone or non-FDA approved effective medications: gabapentin, baclofen, or topiramate) in the 30 days following a positive screen. Denominators will also be derived to represent specific subpopulations (e.g., women, Black and Hispanic Veterans). Rates at the start of the practice facilitation intervention and at 3- and 6-months post intervention will be calculated to examine change in Reach outcomes over time.

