## **5.2 Recruitment Methods**

Ann Arbor regulatory approval is being requested only for the data analysis portion of AIM 3 (extraction, cleaning, and analysis of AIM 3 outcome data from the VA's electronic health record via the Corporate Data Warehouse). All recruitment, enrollment and intervention activities were completed at the Pittsburgh VA.

Approximately 10,000 Veterans' data will be pulled from the CDW to examine implementation and clinical outcomes. Data to evaluate implementation and clinical effectiveness outcomes will be obtained electronically and securely from already collected administrative databases, using scrambled SSN or Patient ICN to link data together. Data sources will include the CDW, Health Factors (AUDIT-C and Brief Intervention information), Vital Status File to obtain DOB for calculating age of Veterans, and Prescription/Pharmacy information (for data on whether medications for alcohol use disorder were prescribed). Other specific records include: sociodemographics (e.g., sex, gender identity, marital status, indicator of socioeconomic status, race/ethnicity, sexual orientation), past-year diagnoses (Alcohol use disorder diagnosis, Substance use disorder diagnoses, Tobacco use disorder diagnosis, Mental Health disorder diagnosis (Depression, anxiety, PTSD, Bipolar, Psychotic-spectrum)), index of medical complexity (e.g., Charlson index, VA CAN score) utilization of primary care services pre-implementation (2019-2022), during (July 2022 - Dec. 2022) and post-implementation intervention (Jan 2023 - Dec. 2023), referral and utilization of substance use services in the past year (yes/no), and referral and utilization of past-year mental health services (yes/no). Data may also be reviewed within CAPRI/Joint Legacy Viewer (JLV) to allow study team members to look into potential data anomalies from our dataset. In addition, members of the study team may review notes, charts, dates of AUDIT-C administration, etc. to verify the accuracy of our Aim 3 dataset.

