#### **5.4 Inclusion/Exclusion Criteria**

We will include all Veterans with a visit to the Pittsburgh VA primary care during the practice facilitation intervention.

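### The AUDIT-C time-series model has no Veteran effect in a cohort fixed by a visit during the intervention, so its standard errors are unreliable and score-related entry or loss could pass for an effect

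*Combined protocol and SAP*

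**What the plan says.** The effectiveness analysis in Section 5.7 compares the clinic with its own past: "we will investigate whether Veterans' with an encounter in Pittsburgh VA Primary Care during the implementation intervention reduced their drinking 12-months post intervention". The model is given in one sentence: "The outcome (AUDIT-C scores) will be modeled using a regression model with an indicator for practice facilitation (pre- vs. post-), a continuous term for time" in days since dissemination, plus the interaction of the two. The indicator is to show an immediate change and the interaction a change in slope.

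Section 5.4 fixes who is in the data: "We will include all Veterans with a visit to the Pittsburgh VA primary care during the practice facilitation intervention". The evaluation part of Section 5.1 sets the extraction window ("The data pull will include data from January 1, 2019 – December 31, 2023") and dates the intervention ("during the course of the practice facilitation intervention (July 2022-December 2022"). The same paragraph labels the comparison period "Rates of alcohol-related care pre-intervention (2019-2022", which runs into the intervention window. Section 5.2 gives the size: "Approximately 10,000 Veterans' data will be pulled from the CDW to examine implementation and clinical outcomes".

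The documents do not state a Veteran effect, a clustered or robust variance, an autocorrelation term, or how missing scores are handled. They do not say whether the regression uses individual scores or period means, or on which day the break falls. Section 5.7 does say that identifiers will be replaced by a study ID, so scores can be grouped by Veteran.

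**The concern.** Every cohort member is in care at some point in July–December 2022. Looking back from there, Veterans join the data over time. Looking forward, they can die, move or stop attending. The selection point therefore lies where the break will be placed, and the mix of Veterans being scored can change differently on its two sides. The plan chose a time series because it takes prior trend into account, but that trend is estimated in Veterans who were all still in care in 2022. It cannot predict how the mix changes afterwards.

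A model without a Veteran effect cannot separate Veterans who drink less from a change in which Veterans are scored. If it is fitted to individual scores with an ordinary error term, it also treats several scores from one Veteran as unrelated, and ignores any shock common to everyone scored in the same month.

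The plan intends this result as preparation for a larger trial. A false decline, or an interval of the wrong width, would feed into that planning.

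**Working it through.** **Inputs.** From the documents: about 10,000 Veterans, data for 2019–2023, intervention July–December 2022, and a model with indicator, days and interaction. They give no attrition, entry, correlation, SD, alpha or power figure, so there is no plan figure to reproduce. Every rate below is an assumption.

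**Step 1. Composition by hand.** Let a share p0 of the cohort be heavier drinkers whose mean AUDIT-C is d points above the rest. If yearly leaving is a for them and b for the others, the share one year later is p1 = p0(1−a) / [p0(1−a) + (1−p0)(1−b)]. The cohort mean moves by d(p1−p0) with no one changing their drinking. With p0 = 0.12:

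- 5% v 5%: 0.114/(0.114+0.836) = 0.1200, a shift of 0.
- 10% v 5%: 0.108/(0.108+0.836) = 0.1144, a shift of −0.0056d.
- 15% v 5%: 0.102/(0.102+0.836) = 0.1087, a shift of −0.0113d.
- 25% v 8%: 0.0900/(0.0900+0.8096) = 0.1000, a shift of −0.0200d.

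**Step 2. The stated model, simulated with no intervention effect.** Assumptions: 10,000 Veterans, about one score a year, 12% heavier drinkers, 40% entering care during 2019–2022, residual SD 1.3, 85% yearly completion, active months excluded. There were 300 runs per setting, then a separately coded repeat of 200 runs under the same general assumptions.

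| Yearly leaving, heavier v others | False 12-month effect | Repeat |
|---|---|---|
| 10% v 5% | −0.04 | −0.041 |
| 15% v 5% | −0.075 | −0.059 |
| 25% v 8% | −0.13 (45% of runs significant) | −0.098 (22%) |

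A further variant of score-related leaving gave −0.02 to −0.08. Within-Veteran estimates were 0.00 in the first set, −0.002 to +0.003 in the repeat and about 0.00 in the variant. Dividing the table by Step 1 (0.04/0.0056 = 7.1 down to 0.098/0.0200 = 4.9) implies d of about 5 to 7 points. The match is approximate, because entry also contributes.

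**Step 3. Dependence on the break date.** A second design used SD 2.5, within-Veteran correlation 0.6 and 200 runs. In the loss rows 20% have no later score; in the entry rows Veterans enter at 0.1 a year. Retention or entry depends on the usual score through log-odds per SD. False-positive rates for the model as stated are in brackets.

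| Dependence on usual score | July 2022 break: slope change per year | January 2023 break: level change |
|---|---|---|
| None (loss and entry unrelated) | −0.001 (1.5%) | −0.016 (4%) |
| Loss, 0.2 | −0.072 (43%) | −0.087 (11%) |
| Loss, 0.5 | −0.184 (100%) | −0.169 (24%) |
| Loss and entry, 0.2 | −0.109 (83%) | −0.089 (11%) |
| Loss and entry, 0.5 | −0.275 (100%) | −0.231 (36%) |
| Entry only, 0.2 / 0.5 | −0.039 / −0.097 | not run |

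The −0.016 in the first row is within simulation error (0.134/√200 = 0.009). In the scenarios with differential loss or entry, a within-Veteran fit with clustered standard errors gave mean slope changes of −0.001 to +0.004 a year (July) and level changes of −0.012 to +0.012 (January). False positives were 3.5–8.5% and 3–7.5%, with simulation error of about 1.5 points.

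**Step 4. Standard errors.** For one score before and one after with correlation ρ, the independent-error variance of the difference is 2σ²/n and the true one is 2σ²(1−ρ)/n. The stated SE is then 1/√(1−ρ) times the true one: 1.20, 1.58 and 2.24 at ρ = 0.3, 0.6 and 0.8. Simulated ratios without attrition:

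- July break: 1.13, 1.51, 1.74 (level) and 1.31, 1.45, 1.82 (slope change).
- January break: 1.01, 1.02, 1.10 (level) and 1.00, 1.02, 1.09 (slope change). With one score a year, each Veteran supplies a single post-break score, so splitting the post period into level and slope compares different Veterans.

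Shared shocks reverse the direction. Under the Step 2 assumptions with equal leaving, the SE is 0.072 against a true SD of 0.059 (0.072/0.059 = 1.22). With monthly shocks of SD 0.10 the true SD is 0.099 (0.072/0.099 = 0.73), with 17% false positives. The repeat gave 0.071 against 0.060, then 0.071 against 0.097 with 12.5% false positives; a shock SD of 0.20 gave 32%. The further variant gave 0.064 against 0.054, then 0.064 against 0.081 with shocks.

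The within-Veteran contrast is also more precise: SD 0.040 against 0.059 without shocks, a variance ratio of (0.040/0.059)² = 0.46.

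**The case against.** **The plan is silent rather than wrong.** It names no error structure and no unit. A reader might infer that the sponsor has decided to pool scores as independent; the text does not say so. Time in days makes individual scores the natural reading, but period means are possible. This limits the standard-error point. It does not remove the composition point, since a monthly mean shifts with the mix of Veterans just as pooled scores do.

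**Attrition alone does nothing.** A reader might infer that a cohort anchored on an intervention-period visit must show a break. It need not: with loss and entry unrelated to AUDIT-C, Steps 1 and 3 show none. Sections 2.0 and 5.5 link unhealthy alcohol use to mortality, which makes score-related loss plausible, but no rate is given.

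**Intervals that are too narrow are not a given.** Under Veteran correlation alone the error is conservative or negligible. The inflated false-positive rates in Step 4 come wholly from assumed monthly shocks.

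**The bias may be small.** With SE 0.072 and true SD 0.059, the two-sided 5% limit is 1.96 × 0.072 = 0.141. A bias of −0.04 then gives about 4–5% rejections ((0.141−0.04)/0.059 = 1.71), and −0.075 about 13% ((0.141−0.075)/0.059 = 1.12). Section 5.1 calls a measurable clinical effect unlikely, and no decision rule hangs on the test. This stands as a limit on severity.

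**A Veteran effect is not a full cure.** The near-zero results follow from simulating loss on a stable trait. Loss that follows a change in drinking would still bias the estimate. A random intercept is not purely within-person either, because it mixes in between-Veteran information.

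**Conclusion.** The point stands in conditional form. As written, the model neither accounts for repeated scores nor separates change in drinking from change in who is scored, and the cohort definition puts the selection window where the break will fall.

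- Standard errors, if individual scores are fitted: from about right to 1.82 times too large under Veteran correlation alone, depending on the break date and the correlation; about 0.73 to 0.79 of their proper size under the assumed monthly shocks.
- False effect: none if entry and loss are unrelated to AUDIT-C. Roughly −0.02 to −0.13 points at 12 months under leaving of 10–25% v 5–8% a year. It is mainly a slope change with a July 2022 break and mainly a level change with a January 2023 break, and selective entry before the window adds to it.

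The documents do not show that the result will be biased; they leave the plan unable to tell. This should be corrected before the analysis, but its pilot purpose keeps it from being critical.

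**What to change.** In Section 5.7:

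1. State the unit of analysis (individual AUDIT-C scores) and the break date, and say how July–December 2022 is treated, since the pre-period label overlaps it.
2. Add Veteran fixed effects using the existing study ID, with Veteran-clustered standard errors. Prefer fixed effects to a random intercept, for the reason given above.
3. Allow for shared calendar-month shocks with a month random effect, or check the result against monthly means with Newey-West standard errors.
4. Report the number of Veterans scored in each period, and repeat the analysis in Veterans scored both before and after the break.
5. State that this removes selection on a stable drinking level only, not drop-out that follows a change in drinking.

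The cost is a change of wording and some extra output from data already requested. The statistical price is small: Veterans scored on only one side contribute little to the contrast, while precision improves. A repeated cross-section of all Veterans seen each month in 2019–2023 is optional. It answers a different question from the one in Section 5.7, and needs a wider extraction and a revised patient count.

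### Both Effectiveness measures pool all attenders regardless of earlier screen result, so an effect confined to Veterans with AUDIT-C ≥5 would be diluted in absolute terms; an index-positive analysis should be added

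*Combined protocol and SAP*

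**What the plan says.** **Who is analysed for Effectiveness.** Section 5.1 (Evaluation of the Practice Facilitation Intervention) defines Effectiveness as a 12-month prevalence with the "denominator defined as all Veterans with a visit to PC during the practice facilitation intervention". Of the numerator it says "The numerator will be the number of Veterans with an encounter in PC who screened positive for unhealthy alcohol use", meaning AUDIT-C ≥5 at 12 months whatever the earlier result. Section 5.7 adds a time-series analysis of AUDIT-C scores: "we will investigate whether Veterans' with an encounter in Pittsburgh VA Primary Care during the implementation intervention reduced their drinking 12-months post intervention". Its regression terms are a pre/post indicator, time and their interaction. There is no term or stratum for earlier screen result. Section 5.4 includes all attenders, and Section 5.2 puts the data pull at about 10,000 Veterans.

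**Who is due the care.** Section 5.1 defines Adoption as "the percentage of providers from the PC clinic who deliver alcohol-related care when a Veteran screens positive for unhealthy alcohol use". The Reach numerator needs AUDIT-C ≥5 and care "in the 30 days following a positive screen". The Reach example in Section 5.7 likewise concerns patients with AUDIT-C ≥5.

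**Subgroups.** Subpopulation denominators are mentioned only for Reach, and the examples are demographic. None is defined by screen result.

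**The concern.** The question in Section 5.7 is whether Veterans cut down their drinking. Under the plan's own Reach and Adoption definitions, a Veteran scoring below 5 does not trigger the care being measured, and one scoring 0 has no drinking to reduce. Pooling these Veterans with the screen-positive ones averages any effect in positives with a group in which little or none is expected.

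The 12-month prevalence also combines two flows: Veterans moving from positive to negative, which care after a positive screen might bring about, and Veterans newly becoming positive, whom such care had not yet reached.

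The result is meant as pilot data for a larger trial. An absolute effect taken from all attenders could be carried into that trial's planning as if it described Veterans who need the care.

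**Working it through.** The plan gives no sample-size calculation, SD, effect size or AUDIT-C prevalence, so there is no figure of its own to reproduce. From the documents come N ≈ 10,000 (Section 5.2, a data-pull size) and the cut-off of 5. Every other input below is an assumption.

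**1. Absolute dilution.** If only the screen-positive share p can respond, the change over all attenders is p × the change in positives, so the dilution is 1/p: 1/0.05 = 20, 1/0.10 = 10, 1/0.20 = 5 and 1/0.33 ≈ 3.

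**2. Mean AUDIT-C.** Assume that receipt of care among positives rises by 20 percentage points and that each additional treated Veteran falls by 1 point. The change in positives is 0.20 × 1 = 0.20. Assume also SD 2.5 in both groups and a simple two-sample comparison with n per period, so SE = √2 × 2.5/√n. For all attenders, SE = 3.536/100 = 0.0354.

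| p | Change, all attenders | Effect/SE, all (n = 10,000) | n positive | Effect/SE, positives | Ratio = 1/√p |
|---|---|---|---|---|---|
| 5% | 0.01 | 0.28 | 500 | 1.26 | 4.5 |
| 10% | 0.02 | 0.57 | 1,000 | 1.79 | 3.2 |
| 20% | 0.04 | 1.13 | 2,000 | 2.53 | 2.2 |

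The loss in effect/SE is 1/√p rather than 1/p, because the larger group partly compensates. It also depends on the SDs. With 3.5 in positives and 2.0 overall, the ratio is multiplied by 2.0/3.5, giving 4.5 × 0.571 ≈ 2.6 at p = 5% and 2.2 × 0.571 ≈ 1.3 at p = 20%.

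**3. Prevalence.** Let s be the share of index positives still positive at 12 months and i the onset among index negatives. Then 12-month prevalence = p·s + (1 − p)·i.

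*Large effect.* Take s falling from 70% to 50%. In positives this is 20 points, or 20/70 = 28.6% in relative terms. With p = 10% and i = 2%, prevalence falls from 0.070 + 0.018 = 8.8% to 0.050 + 0.018 = 6.8%. That is 2.0 points, and 2.0/8.8 = 22.7% relative. Over p = 5–20% and i = 1–5%, the absolute fall is 1 to 4 points, while the relative fall is 12% to 27%. New cases make up between 7% and 66% of the 12-month positives.

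*Small effect.* Take s falling from 70% to 65%, with i = 2%, two-sided 5% tests and independent periods.

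| p | Difference, all | Power, all (10,000 per period) | Difference, positives | Power, positives (n per period) |
|---|---|---|---|---|
| 5% | 0.25 points | 12% | 5 points | 39% (500) |
| 10% | 0.5 points | 24% | 5 points | 67% (1,000) |
| 20% | 1.0 point | 51% | 5 points | 92% (2,000) |

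These comparisons show direction and rough size only. The planned model is a segmented regression, and the positive-group counts assume that every index positive is screened again.

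**The case against.** The strongest reply is that facilitation is a clinic-level strategy evaluated under RE-AIM, and that Effectiveness was deliberately given the Reach denominator. Clinic-wide prevalence is a legitimate estimand, and netting resolution against onset is what prevalence does. This stands, and is why the all-attender analyses should stay.

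Second, care is not shown to be confined to positives. Section 5.1 describes patient handouts and motivational-interviewing training without expressly limiting them to screen-positive Veterans. Some effect outside that group is possible, so the 1/p factor is conditional.

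Third, the stakes are modest. Section 5.1 already says that a measurable clinical impact is unlikely, and Section 5.7 describes the analysis partly as a training opportunity. But the plan attributes the low expectation to this being a pilot and does not mention dilution. The reply lowers the priority of the point without answering it.

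Fourth, selecting Veterans on a high score brings regression to the mean, and the 2022 selection uses screens taken while facilitation was under way. Both are real costs, and the change must deal with them. They argue against replacing the trend-adjusted series with an index-positive contrast, but not against adding one beside it.

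A reader might infer that the all-attender result will be near zero whether or not the care works, and so cannot inform a larger trial. The documents do not support that. The relative change in prevalence survives largely intact when onset is low, and an all-attender series still supplies prevalence, score SD, historical trend and screening completeness.

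**Conclusion.** The mismatch is on the face of the text: the measured care depends on a positive screen, while both Effectiveness measures ignore screen history. If the effect is confined to screen-positive Veterans, the mean change and the absolute prevalence change are diluted by 1/p, or 5- to 20-fold for an assumed p of 5–20%. Effect/SE is lower by about 1/√p with equal SDs (2.2 to 4.5 times), and by less if positives are more variable. The several-fold figure should not be read as a loss of power, nor applied to relative prevalence, which only new-onset cases weaken. It is also not a documented figure, since the plan gives no prevalence.

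This is a worthwhile improvement to how the plan answers its own question. It does not invalidate the clinic-level estimate.

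**What to change.** 1. Keep the all-attender prevalence and the time-series model as the clinic-level estimate.
2. Add a prespecified Effectiveness analysis among Veterans with an index AUDIT-C ≥5 in July–December 2022. Report the change in AUDIT-C and the proportion falling below 5 at a fixed follow-up interval. Report new onset among index-negatives separately.
3. Apply the identical index rule and interval to pre-facilitation July–December cohorts within the 2019–2023 pull, and extend the Section 5.4 inclusion rule to those Veterans. Interpret the 2022 change only against these cohorts, never on its own.
4. State the all-attender effect on both the absolute and the relative scale, with the observed share screening positive.

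**Cost.** Protocol wording and a wider query on the same tables and dates; extraction and analysis are the activities still to be completed. Downsides to state in the plan:

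- There are fewer Veterans in this analysis, and it depends on rescreening, for which the documents give no rate.
- At a 12-month interval, the July–December 2021 cohort is followed up in July–December 2022, entirely during facilitation, so it is not a clean comparator. Mainly the 2019 and 2020 windows remain, with a calendar-period caveat.
- If facilitation changed who was screened or how answers were recorded, the 2022 positives may not be comparable with earlier positives. Screening completeness and the share screening positive should be shown by cohort.
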